### **6.5.2. Exposure for Cabozantinib/Placebo Component**

Exposure for cabozantinib/placebo treatment will be summarized as follows:

- Duration of exposure (including dose holds) calculated as (earlier of date of decision to discontinue oral component or cutoff date – date of first dose of oral component + 1) /30.4375
- Duration of exposure (excluding dose holds) calculated as (earlier of date of decision to discontinue oral component or cutoff date – date of first dose of oral component - total days with oral dose received of 0 mg + 1) /30.4375
- Average daily dose (mg/day) calculated as (total mg received/duration of exposure in days)
- Percent dose intensity, calculated as  $100 \times (\text{average dose in mg/day})/(40 \text{ mg/day})$

### **6.5.3. Exposure for Nivolumab Treatment Component**

Exposure for nivolumab will be summarized as follows:

By descriptive statistics:

- Duration (in months) of exposure including delays calculated as (date of last infusion of nivolumab – date of first dose of nivolumab)/30.4375
- Number of infusions administered per subject
- Number of expected infusions per subject
- Cumulative dose

- Average dose (mg/infusion)
- Overall relative dose intensity (%)
- Relative dose intensity (%) for infusions 1-4 (weight based)
- Relative dose intensity (%) for infusions 5 onwards (flat dose received)

By frequency count and percent:

- Duration (in months) of exposure including delays categorized as 0-3m, > 3m-6m, > 6m-12m, > 12m-24m, > 24m
- Number of infusions administered per subject categorized as 0, 1-4, 5-10, 11-16, 17-22,  $\geq 23$
- Number of subjects with any incomplete nivolumab infusions
- Number of subjects with interrupted nivolumab infusions

#### **6.5.4. Exposure for Ipilimumab Treatment Component**

Exposure for ipilimumab will be summarized as follows:

By descriptive statistics:

- Duration (in months) of exposure including delays calculated as (date of last infusion of ipilimumab – date of first dose of ipilimumab)/30.4375
- Number of infusions administered per subject
- Number of expected infusions per subject
- Cumulative dose
- Average dose (mg/infusion)
- Overall relative dose intensity (%)

By frequency count and percentage for:

- Number of subjects completing ipilimumab treatment
- Number of subjects discontinuing ipilimumab early. Amongst these subject's categorical summary for number of doses received (1, 2, 3)
- Number of subjects continuing ipilimumab. Amongst these subject's categorical summary for number of doses received (1, 2, 3)
- Number of ipilimumab infusions received: 0, 1, 2, 3, 4
- Number of subjects by cycles of ipilimumab administered: 0, 1, 2, 3, 4
- Number of subjects with any incomplete ipilimumab infusions

- Number of subjects with interrupted ipilimumab infusions

## 6.6. Study Treatment Modifications

Treatment modifications will be summarized separately for each component and will include subjects in the Safety and P-Safety populations. For cabozantinib/placebo treatment components treatment modifications includes holds and reductions, for nivolumab/ipilimumab treatment components they include infusion delays. Treatment modifications only due to AE will be summarized. Note that incomplete or interrupted infusions will be summarized separately and will not be considered as treatment modifications.

### 6.6.1. Dose Reduction due to Adverse Events

Dose reductions are permitted for cabozantinib or placebo but not for nivolumab or ipilimumab. Two dose reduction levels for the oral study medication are 20 mg qd and 20 mg every other day [qod]. The following summaries for dose reductions due to AE by treatment arm will be presented:

Categorical summaries for:

- Subjects with any dose reduction
- Dose level received by a subject (40 mg, 20 mg qd, 20 mg qod)
- Lowest non-zero dose level received
- Last dose level received (excluding dose holds)
- Last dose level received (including dose holds)

Descriptive statistics for:

- Duration of treatment in months for each dose level received per subject
- Time from first dose to first dose level reduction (days)
- Time from first dose to second dose level reduction (days)

### 6.6.2. Dose Holds (Delays) due to Adverse Events

Nivolumab or ipilimumab infusion may be delayed. An infusion was considered delayed if the delay exceeded by 3 days for nivolumab/ipilimumab. For cabozantinib/placebo dose was considered as held if the subject did not take the dose of the medication. The following hold/delay summaries due to AE for study treatment, both infusion components due to the same AE and each treatment component will be presented:

- Subjects with any dose delay/hold
- Frequency counts and percentages for subjects with any dose hold, hold  $\geq$  7 days,  $\geq$  14 days,  $\geq$  21 days
- Descriptive statistics for number of dose holds (0 mg dose level) due to an AE per subject and classified as 1, 2, 3, and  $>3$
- Descriptive statistics for total duration of dose holds per subject due to an AE, where duration of each dose hold is calculated as (stop date of hold – start date of hold + 1). Categorical summaries for  $\geq$  7 days,  $\geq$  14 days, and  $\geq$  21 days will also be presented
- Descriptive statistics for duration of each dose holds due to an AE, calculated as (stop date of hold – start date of hold + 1). Categorical summaries for  $\geq$  7 days,  $\geq$  14 days, and  $\geq$  21 days will also be presented
- Descriptive statistics for time to first dose hold (also presented for study treatment), time to first dose hold that was  $\geq$  7 days,  $\geq$  14 days, and  $\geq$  21 days. The time to dose hold is calculated as (start date of the hold – first dose date + 1)
- Descriptive statistics for time to second dose hold, time to second dose hold that was  $\geq$  7 days,  $\geq$  14 days, and  $\geq$  21 days

### **6.6.3. Dose Modifications due to Adverse Events**

For cabozantinib a subject may experience three types of dose modifications (dose reductions to 20 mgs qd or 20 mgs qod, and dose holds) due to an AE. For nivolumab/ipilimumab dose modifications include infusion delays due to AE. Thus, the maximum number of dose modification types a subject may experience is four. The following summaries will be presented per treatment arm:

- Frequency counts and percentages for subjects with any dose modifications
- Descriptive statistics for number of dose modification types (0-4)
- Descriptive statistics for time to the first dose modification
- Descriptive statistics for time to the second dose modification

### **6.7. Incomplete or Interrupted Infusions**

The following summaries will be presented for infusion components and will include subjects in the Safety arm:

- Number of subjects with any incomplete ipilimumab infusions
- Number of subjects with interrupted ipilimumab infusions

- Number of subjects with any incomplete nivolumab infusions
- Number of subjects with interrupted nivolumab infusions

## **6.8. Study Treatment Non-Compliance and Dosing Errors**

Treatment non-compliance and dosing errors for reasons other than AE will be summarized in the Safety population. Frequency counts and percentages will be presented by treatment groups for:

- Subjects with dose hold/delay (0 mg) due to non-compliance
- Subjects who received dose > maximum allowed dose level at any time (40 mg qd for cabozantinib, 480 mg per infusion for nivolumab, > 1mg/kg mg per infusion for Ipilimumab)
- Subjects who received non-protocol specified dose level ( $\leq$  maximum allowed dose level) at any time due to non-compliance, or due to site/logistic error or other reason

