## **6.2 Study Treatment Schedule of Administration**

Two tablets of cabozantinib (20 mg each) or matched placebo once-daily (qd) will be administered orally.

CONFIDENTIAL

Protocol XL184-313 Protocol Amendment 3.0  
Page 80 of 193

Nivolumab will be administered at a dose of 3 mg/kg as an IV infusion once every 3 weeks (q3w) for the first four doses followed by the standard dosing regimen of 480 mg as an IV infusion once every 4 weeks (q4w) for no more than 2 years.

Ipilimumab will be administered at a dose of 1 mg/kg as an IV infusion q3w for a maximum of up to four doses. Subjects will receive the combination regimen with the first infusion of nivolumab and ipilimumab given on the same day as the first dose of cabozantinib or placebo.

The dose of nivolumab and ipilimumab will need to be adjusted based on the subject's current body weight on study should a change of at least 10% compared with baseline be documented.

Subjects will receive oral study treatment and (up to 2 years) nivolumab as long as they continue to experience clinical benefit as assessed by the Investigator or until unacceptable toxicity, the need for subsequent systemic anti-cancer treatment, or until any other reasons for treatment discontinuation listed in the protocol ([Section 3.6](#)).

For guidance on dose modifications, interruptions, delays, or discontinuations due to AEs, refer to [Section 6.6.2](#) for cabozantinib and [Section 6.6.3](#) for nivolumab/ipilimumab.

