## **6.2.1 Study Treatment Administration on Week 1 Day 1 (W1D1)**

### Nivolumab and Ipilimumab:

Doses of nivolumab (3 mg/kg) will always be administered IV at the clinic by infusion on Day 1 of each 21-day cycles for the first 4 doses. Thereafter, doses (480 mg) will be administered on Day 1 of each 28-day cycle. In this study, treatment with nivolumab will be given for a maximum of 2 years from the start of study treatment.

Doses of ipilimumab (1 mg/kg) will always be administered IV at the clinic by infusion on Day 1 of each 21-day cycles for a maximum of four doses. Cycles may be longer if nivolumab or ipilimumab treatment is delayed due to toxicity or other reasons.

When nivolumab and ipilimumab are to be administered on the same day, nivolumab is to be administered first. Nivolumab infusion (approximately 30 minutes) must be promptly followed by a saline flush to clear the line of nivolumab before starting the ipilimumab infusion. The second infusion will always be ipilimumab study drug (approximately 30 minutes infusion) and will start after the infusion line has been flushed and participant has been observed to ensure no infusion reaction has occurred. The time in between infusions is expected to be approximately 30 minutes (from the end of the nivolumab infusion to the start of the ipilimumab infusion).

CONFIDENTIAL

Protocol XL184-313 Protocol Amendment 3.0  
Page 81 of 193

On W1D1, nivolumab and ipilimumab are to be administered before the oral study treatment.

The infusion of nivolumab and ipilimumab will be prepared according to the local prescribing information or the pharmacy manual. The IV administration of nivolumab and ipilimumab can only occur in a clinical setting with staff experienced in managing of infusion-related reactions and with access to emergency services.

Subjects should be carefully monitored for infusion reactions during IV administration. If an acute infusion reaction is noted, participants should be managed according to [Section 6.6.3](#).

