### **6.6.3 Management of AEs Associated with Nivolumab and Ipilimumab**

The assigned dose for nivolumab is 3 mg/kg IV q3w for the first four doses followed by 480 mg IV q4w.

The assigned dose for ipilimumab is 1 mg/kg IV q3w for a maximum of up to four doses.

Dose reductions are not allowed for nivolumab or ipilimumab. AEs associated with nivolumab and ipilimumab are managed with dose delays.

For more detailed guidance on management of non-hepatocellular AEs associated with nivolumab and ipilimumab please see [Appendix E](#). For recommendations on management of hepatocellular toxicity and dose modifications of both cabozantinib/placebo treatment and nivolumab/ipilimumab treatment, see [Section 6.6.1](#)

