**Table 5: Study Therapy Definitions (Weight Based Cycles 1-4)**

	Nivolumab	Ipilimumab	Cabozantinib/Placebo
Intended dose for each cycle (i) for infusion components and in mgs for oral components	3 mg/kg/3wk for i=1-3; 3 mg/kg/4wk for i=4	1 mg/kg/3wk for i=1-4	40 mg once daily
Dose (i)	Total dose administered in mgs for each cycle is collected on the CRF	Total dose administered in mgs for each cycle is collected on the CRF	Total dose for the interval is collected on the CRF
Cycle duration (i) (wk)	(Dose date (i+1) - Dose date (i) )/7 for i=1-3 i=4, 28/7=4 wks	(Dose date (i+1) - Dose date (i) )/7 for i=1-3 i=4, 21/7=3 wks	NA
Cycle intensity (i) (mg/kg/wk)	Dose (i) /Cycle duration (i) i=1-4	Dose (i) /Cycle duration (i) i=1-4	NA
Relative cycle intensity (i) (%)	(Cycle intensity (i) / intended dose (i) ) × 100 for i=1-4	(Cycle intensity (i) / intended dose (i) ) × 100 for i=1-4	NA
Relative dose intensity (%)	Sum of all relative cycle intensities divided by number of weight-based infusions received	Sum of all relative cycle intensities divided by number of weight-based infusions received	See Table 4

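### SAP 6.8 applies one 480 mg limit to every nivolumab infusion, so excess doses in the four weight-based infusions are largely misclassified in the dosing-error table

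*SAP*

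**What the plan says.** SAP 6.8 plans frequency counts in the Safety population for dosing problems not due to adverse events. One row is for "Subjects who received dose > maximum allowed dose level at any time (40 mg qd for cabozantinib, 480 mg per infusion for nivolumab". The only nivolumab limit it gives is thus "480 mg per infusion for nivolumab", with no split by dosing phase. The same bullet gives ipilimumab a per-kg limit: "> 1mg/kg mg per infusion for Ipilimumab". The following row is for "Subjects who received non-protocol specified dose level", restricted to levels at or below the maximum and covering non-compliance, site or logistic error, and other reasons.

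Protocol 6.2 states: "Nivolumab will be administered at a dose of 3 mg/kg as an IV infusion once every 3 weeks (q3w) for the first four doses". Protocol 6.6.3 repeats it: "The assigned dose for nivolumab is 3 mg/kg IV q3w for the first four doses". The flat dose comes later, in Protocol 6.2.1: "Thereafter, doses (480 mg) will be administered on Day 1 of each 28-day cycle". The SAP's exposure section follows the protocol: Table 5 sets the intended nivolumab dose at "3 mg/kg/3wk for i=1-3; 3 mg/kg/4wk for i=4", and Table 6 uses 480 mg only from cycle 5.

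**The concern.** The 480 mg limit belongs to the second dosing phase but is applied to both. In infusions 1 to 4 the assigned dose depends on weight and is below 480 mg for anyone under 160 kg, so a dose can be well above assignment without crossing the limit.

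Protocol 8.5.2 treats any administration outside or above the established regimen as a medication error. An early infusion above 3 mg/kg meets that definition whether or not it passes 480 mg. At stake is whether the row for doses above the maximum describes what it claims to describe in the period when nivolumab and ipilimumab are given together.

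**Working it through.** **Inputs**
- Limit: more than 480 mg, any infusion (SAP 6.8).
- Assigned dose: 3 mg/kg for infusions 1 to 4, 480 mg flat afterwards (Protocol 6.2, 6.2.1, 6.6.3; SAP Tables 5 and 6).
- Body weight: the documents give no distribution, so weights below are illustrative or assumed.

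**Where the limit agrees with the assigned dose.** From infusion 5 the two are the same figure. In infusions 1 to 4 they agree only at 480/3 = 160 kg.

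**When the row counts an early dose.** Let w be weight in kg and r the ratio of given to assigned dose. The dose given is r × 3w, so the row counts it only if r × 3w > 480, that is r > 160/w.

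| Weight (kg) | Assigned dose (mg) | Largest uncounted multiple |
|---|---|---|
| 60 | 180 | 2.67 |
| 80 | 240 | 2.0 |
| 100 | 300 | 1.6 |
| 120 | 360 | 1.33 |
| 160 | 480 | 1.0 |

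Two special cases follow:
- Giving the later flat dose during infusions 1 to 4 is never counted, because 480 is not greater than 480. At 80 kg that is 480/80 = 6 mg/kg, twice the assigned dose.
- At 170 kg the assigned dose is 3 × 170 = 510 mg, so a correct dose is counted as above the maximum.

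**How many subjects this could affect.** An excess of ratio r goes uncounted when w ≤ 160/r. Assuming normally distributed weights with mean 70 to 90 kg and SD 15 to 20 kg, at least 99.98% of subjects weigh under 160 kg, and:

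| Given / assigned | Uncounted up to (kg) | Share uncounted |
|---|---|---|
| 1.10 | 145.5 | 99.7 to 100% |
| 1.25 | 128 | 97 to 100% |
| 1.50 | 106.7 | 80 to 99% |
| 2 | 80 | 25 to 75% |
| 3 | 53.3 | 1 to 20% |

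**Whether relative dose intensity would show these doses.** SAP 6.5.3 summarises it separately for infusions 1 to 4. Table 5 divides each dose by the actual cycle length and averages over infusions. One doubled dose given on time among four gives (200 + 100 + 100 + 100)/4 = 125%. If the next infusion after a doubled dose comes at 6 weeks instead of 3, that cycle's intensity is 6 mg/kg over 6 weeks = 1 mg/kg/week. This equals the intended 3 mg/kg over 3 weeks, so the cycle reads 100%. The measure can hint at excess dosing but does not count subjects who had it.

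**The case against.** The strongest reply is that SAP 6.8 has a second row. An early dose above 3 mg/kg but not above 480 mg is, on a natural reading, an off-protocol level within the maximum, and would be counted there. Early dosing is also visible through relative dose intensity, average dose per infusion and cumulative dose. Protocol 8.5.2 requires reporting of overdoses that lead to adverse events and prompt contact with the Medical Monitor for any overdose, and protocol deviations are tracked separately (SAP 9).

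Much of this stands. A reader might infer that early nivolumab overdoses are missed for nearly all subjects and that the table is falsely reassuring. The documents do not support that: the second row probably captures many of these doses, and large excesses still cross 480 mg in heavier subjects. What remains is misclassification. The second row labels an excess as within the maximum, mixes it with under-dosing, and does not say how a weight-based dose is judged against a level. An early 480 mg dose is especially ambiguous, because 480 mg is itself a protocol level.

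The contrast with ipilimumab's per-kg limit is weak evidence of error. Ipilimumab has no flat-dose phase, so no other limit was possible, and 480 mg can be read as nivolumab's highest flat level. The case rests on the conflict with Protocol 6.2 and SAP Table 5, not on that contrast.

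**Conclusion.** The rule is wrong as written, and the matter is minor. The single limit does not match the assigned dose in infusions 1 to 4, so the above-maximum row omits excess doses that fall at or below 480 mg and would include correct doses in any subject above 160 kg.

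That nearly all modest excesses (up to about 25%) are misclassified depends on nearly all subjects weighing under 160 kg, which is an assumption. The shares for larger excesses depend on the assumed weight distributions; under them, a doubling would still be flagged in 25 to 75% of subjects and a tripling in 80 to 99%. The existence of the conflict needs no weight assumption.

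The effect is confined to a descriptive safety table. Both arms follow the same nivolumab schedule, and SAP 8 plans no formal safety comparison.

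**What to change.** Reconcile SAP 6.8 with Protocol 6.2 and SAP Tables 5 and 6:
- Define the nivolumab maximum by phase as the protocol-assigned dose for that infusion: weight-based for infusions 1 to 4, flat from infusion 5.
- Name the dosing weight: baseline, or the weight updated under the rule in Protocol 6.2 that requires adjustment once weight has changed by at least 10%. This matters because a subject who has lost 9% and is still dosed on baseline weight receives 3/0.91 = 3.30 mg per kg of current weight, and would be flagged if current weight were used.
- State a rounding tolerance.
- Apply the same phase split to the row for off-protocol levels, so that excess and under-dosing can be told apart.

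The cost is SAP wording and a small programming change. Table 5 says the administered dose per cycle is on the CRF, weight is summarised in SAP 8.8, and the ipilimumab per-kg limit already needs it. If the weight used to prepare each dose is not a CRF field, which the documents do not say, it can be derived from baseline and visit weights. The change corrects an analysis flag only and proposes no dose.

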#### **6.6.3.1 Immune-related Adverse Events (irAEs)**

The immune-modulating properties of ICIs, such as the anti-PD-1 antibody nivolumab, and anti-CTLA-4 antibody ipilimumab are able to undermine immunologic tolerance and generate a subset of AEs (called immune related AEs or irAEs) with an autoimmune inflammatory pathomechanism. IrAEs may involve every organ or tissue (Michot et al 2016). Most irAEs occur within the first 12 weeks of exposure to ICIs but some of them may appear with a delayed onset. Diagnosis of irAEs should be based on exposure to an ICI and a reasonable immune-based mechanism of the observed AE. Whenever possible, histologic examination or other immune-based diagnostic evaluations should be used to support the diagnosis. Other etiologic causes including AEs from tumor progression should be ruled out.

The spectrum of irAEs is wide and can be general or organ-specific. Examples of general irAEs in subjects treated with ICIs such as nivolumab are fatigue, fever, and chills. Organ-specific irAEs consist of pneumonitis, colitis, hepatitis, nephritis and renal dysfunction, skin adverse reactions, encephalitis, myocarditis, and endocrinopathies (hypophysitis, adrenal insufficiency, hyperglycemia).

Early recognition and management of irAEs associated with immuno-oncology agents may mitigate severe toxicity. Medical management of irAEs focuses on suppressing the immune response with non-steroidal and steroid anti-inflammatory medication. Management algorithms have been developed and should be followed for subjects with suspected irAEs. Further information on management of nivolumab/ipilimumab-associated irAEs is provided in [Section 6.6.3.2](#) and [Appendix E](#), and can also be found in the US PI.

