### **8.5.2 Medication Errors/Overdose**

Medication error is defined as the administration of each study drug medication outside or above the established dosing regimens per the specific protocol.

Any study medication overdose, misuse, abuse, or study medication error (excluding missed doses) that results in an AE or SAE requires reporting to the Sponsor or designee according to the guidance for AE and SAE reporting ([Sections 8.1](#) and [8.2](#), respectively).

In case of overdose, the Sponsor Medical Monitor or designee should be contacted promptly to discuss how to proceed. Any AEs that occur as a result of an overdose have to be treated according to clinical standard practice. Please refer to the cabozantinib Investigator Brochure for additional management recommendations regarding overdoses of cabozantinib and to [Appendix E](#) regarding overdoses of nivolumab or ipilimumab.

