## Appendix A: Schedule of Assessments (continued)

Assessment:	Pre-randomization	Screening a (before randomization)	Post-randomization										First Post-Treatment Follow-Up Visit (FU-1; 30±14 days after decision to discontinue study treatment) m	Second Follow-Up Visit (FU-2; 100±14 days after decision to discontinue study treatment) m			
			( $\pm$ 3 Days)														
			W 3 D 1	W 4 D 1	W 6 D 1	W 7 D 1	W 9 D 1	W 10 D 1	W 12 D 1	W 14 D 1							
Adverse events (Section 8)			Document new or worsening AEs from informed consent for SAEs and from first dose for nonserious AEs. Continue monitoring through 30 days (100 days for unrelated SAEs [Table 8-1]) after the date of the decision to permanently discontinue study treatment. AE information will be collected at study visits and may also be collected at any time over the phone or by spontaneous subject report. On W1D1 AEs will be documented pre- and post-dose. Related AEs leading to study treatment discontinuation, AESIs (regardless of causality), and related SAEs are to be followed until resolution, $\leq$ Grade 2 severity, or determination by the Investigator that the event is stable or irreversible (see Section 8.3).														
Cabozantinib / Placebo dosing (Section 6.1.1.1 / 6.1.1.2)			Cabozantinib or placebo tablets given on W1D1 after nivolumab/ipilimumab infusion. Taken once daily at home thereafter until study treatment is discontinued.														
Nivolumab dosing (Section 6.1.1.3; weight-based dose W1D1, W4D1, W7D1, W10D1, flat dose from W14D1 onwards)		X		X		X		X			Nivolumab will be administered as an IV infusion at the clinic W14D1 and every 4 weeks until treatment is discontinued (to a maximum of 2 years).						
Ipilimumab dosing (Section 6.1.1.3; weight-based dose W1D1, W4D1, W7D1, W10D1)		X		X		X		X			No further doses						
Dispense/return of oral study drug and compliance accounting (Section 6.5) b		X		X		X		X		X	Every 4 weeks (W18D1, W22D1 etc)						
Additional systemic anti-cancer treatment and survival status (Sections 5.7.12)			All treated subjects will be contacted at each post-treatment visit, including FU-1, FU-2, and every 12 weeks (+ 14 days) after FU-2 visit until death. Any subjects who are randomized but not treated will be contacted every 12 weeks post-randomization until death.														

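### SAP 6.8 uses a single 480 mg nivolumab ceiling for all infusions, so overdoses in the 3 mg/kg infusions 1-4 are reported as at or below the maximum

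*SAP*

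**What the plan says.** SAP 6.8 summarises non-compliance and dosing errors in the Safety population by treatment group. One row counts subjects whose dose exceeded the maximum allowed level at any time. The limits given are 40 mg daily for cabozantinib, "480 mg per infusion for nivolumab", and a per-kilogram limit of 1 mg/kg for ipilimumab. The next row, which opens "Subjects who received non-protocol specified dose level", covers doses at or below that maximum that were not a protocol level, whether through non-compliance, site or logistic error, or another cause.

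The protocol gives nivolumab in two phases. Section 6.2 states: "Nivolumab will be administered at a dose of 3 mg/kg as an IV infusion once every 3 weeks (q3w) for the first four doses". The flat 480 mg dose every 4 weeks follows. Appendix A fixes the visits: "weight-based dose W1D1, W4D1, W7D1, W10D1, flat dose from W14D1 onwards".

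Elsewhere the SAP respects this split. Table 5 sets the intended nivolumab dose for cycles 1-4 as "3 mg/kg/3wk for i=1-3; 3 mg/kg/4wk for i=4", Table 6 covers the flat-dose cycles from 5 onwards, and section 6.5.3 summarises the first four infusions on their own ("Relative dose intensity (%) for infusions 1-4 (weight based").

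**The concern.** For infusions 1-4 the maximum allowed dose is 3 mg/kg, not 480 mg. The single ceiling is the right number only from infusion 5. The ipilimumab limit in the same bullet is per kilogram, and the SAP's exposure tables separate the phases, so this looks like a drafting omission rather than a deliberate choice.

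The regimen also makes one particular mistake easy: giving the flat 480 mg dose too early. Because the rule requires a dose strictly above 480 mg, that mistake is never counted as above the maximum, whatever the subject weighs. Protocol 8.5.2 defines a medication error as dosing "outside or above the established dosing regimens per the specific protocol", and for the first four infusions the established regimen is 3 mg/kg.

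What is at stake is the accuracy of the overdose row during the combination phase. All four infusions (Weeks 1, 4, 7 and 10) fall in the period about which Protocol 6.6.3.1 says "Most irAEs occur within the first 12 weeks of exposure to ICIs". A reader weighing early toxicity against dosing errors would see nivolumab overdoses labelled as within the maximum.

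**Working it through.** **Inputs.** SAP 6.8: flag if dose > 480 mg, any infusion. Protocol 6.2 and 6.6.3: assigned dose = 3 mg/kg x weight for infusions 1-4, then 480 mg. SAP Table 5: relative cycle intensity = (dose / cycle duration) / intended dose rate, averaged over the weight-based infusions received. The body weights below are examples.

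**Where the stated limit is right.** From infusion 5 the assigned dose is 480 mg, so the limit matches the protocol.

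**Where it is not.** For infusions 1-4 the limit equals the assigned dose only when 3 x weight = 480, that is, at 480 / 3 = 160 kg.

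| Weight | Assigned dose (3 mg/kg) | 480 mg in mg/kg | 480 mg / assigned dose | Is 480 mg flagged by SAP 6.8? |
|---|---|---|---|---|
| 60 kg | 180 mg | 8.0 | 2.67 | No |
| 80 kg | 240 mg | 6.0 | 2.00 | No |
| 100 kg | 300 mg | 4.8 | 1.60 | No |
| 120 kg | 360 mg | 4.0 | 1.33 | No |
| 160 kg | 480 mg | 3.0 | 1.00 | No (correct) |

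A full doubling (6 mg/kg) stays at or below 480 mg for weights up to 480 / 6 = 80 kg. Between 80 and 160 kg, smaller overdoses escape.

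**The opposite error.** At 165 kg the compliant dose is 3 x 165 = 495 mg, which exceeds 480 mg and is counted as an overdose.

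**Would the infusion 1-4 dose intensity show it?** One doubled dose with all four infusions on time gives (100 + 200 + 100 + 100) / 4 = 125%. If the doubled dose is one of infusions 1-3 and the next infusion comes after 6 weeks instead of 3, that cycle's intensity is 6 mg/kg / 6 wk = 1 mg/kg/wk against an intended 3 mg/kg / 3 wk = 1 mg/kg/wk. That is 100%, and the overdose disappears from the summary.

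**With the limit set by phase.** At 80 kg the limit for infusions 1-4 becomes 240 mg, and a 480 mg infusion is counted as above the maximum.

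**The case against.** The strongest reply is that nothing is lost. A mistaken 480 mg dose at infusion 2 still appears in the next row of the same table, so the fault is one of placement. Other summaries could also reveal it. SAP section 4 reports minima and maxima for continuous data, so a 125% dose intensity could show as the maximum in the section 6.5.3 summary, and the 100% case needs a delay of exactly three weeks after the overdose. Protocol 8.5.2 asks for prompt contact with the medical monitor after an overdose, and SAP section 9 summarises important protocol deviations, although the plan defining these is not available here. No irAE or AESI analysis draws on the 6.8 counts. Nothing in the documents shows that any subject weighs over 160 kg.

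Most of this is fair and limits the consequence. It does not repair the row. The next row pools overdoses with underdoses and describes them all as at or below the maximum. A maximum dose intensity gives no number of overdosed subjects.

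A second reply concerns the remedy. A bare limit of more than 3 mg/kg could produce false flags, because Protocol 6.2 requires a dose change only when weight has changed by at least 10%. A subject who has lost 9% and correctly stays on the baseline dose receives 3 / 0.91 = 3.30 mg/kg of current weight. This point stands, and the reference weight must therefore be defined.

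**Conclusion.** The concern holds. As written, SAP 6.8 misclassifies nivolumab doses above 3 mg/kg and up to 480 mg in infusions 1-4 for every subject under 160 kg. At 80 kg that range runs up to twice the assigned dose, and at 60 kg up to 2.67 times. This follows from the written limit and the protocol dose; the only assumption is the choice of example weights. How many subjects would be affected cannot be judged from the documents.

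The point is minor. It concerns one descriptive safety table. Nivolumab is scheduled identically in both arms, so no direction of imbalance is claimed.

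**What to change.** In SAP 6.8, replace the single nivolumab limit with two: more than 3 mg/kg for infusions 1-4, and more than 480 mg from infusion 5. This reuses the split in SAP Tables 5 and 6.

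In the programming specifications or an addendum, which SAP 4.8 allows for clarifications and minor corrections, define the reference weight for both per-kilogram limits (nivolumab infusions 1-4 and ipilimumab). It should be the dosing weight under Protocol 6.2: baseline weight, updated when the change reaches 10%. Add a rounding allowance chosen by the sponsor. A separate listing of doses left unadjusted after a weight change of 10% or more would be useful but is optional.

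The phase split costs one phrase. The weight definition and rounding allowance add a short specification. A body weight is already needed for the ipilimumab limit and for the mg/kg/wk intensities in Table 5, so no further data collection is required.
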